4.3.3. Seroresponse Rate of ELISA Titers and PsVNT

Seroresponse is defined as a \geq 2-fold increase in the titer when compared to baseline (Day 1). If the baseline titer is <LLOQ or <LOD (ELISA only), a seroresponse is defined as titer greater than or equal to LLOQ.

The number, percent, and associated exact 95% CI of subjects whose baseline response is negative, i.e., less than the LLOQ, will be tabulated for each treatment group and the combined PHV01 vaccine group.

The number, percent, and exact 95% CI of seroresponse for Days 8 (if tested), 15, 29, 85 and 181 will be calculated. Comparisons between each PHV01 dose level with one another and with the placebo group will be performed using the Newcombe method.

Analyses of seroresponse rates will be performed separately for the ELISA IgG and neutralizing antibody titers.

4.3.4. Correlation between IgG ELISA and neutralizing antibody titers on Days 29, 85 and 181

Spearman's rank correlation will be used to estimate the association between IgG antibody titers and PsVNA titers for each PHV01 vaccine dose group including the combined PHV01 group at Days 29, 85, and 181.

4.4. Safety Analyses

Safety analyses will be conducted using the ASaT population.

4.4.1. Study Vaccine/Placebo Exposure

Within each vaccine group, dosing information for each subject will be presented in a data listing.

4.4.2. Adverse Events

AEs will be assessed by evaluating reactogenicity (local reactions and systemic reactions) and the occurrence of post-vaccination solicited local reactions and systemic AEs through day 15. Solicited AEs for days 16-29 are limited to instances of neurological signs and symptoms, arthritis, and rash. Arthritis, rash, and neurologic events should be evaluated throughout the study and may include expert consultation.

All AEs (including solicited AEs) will be coded using the MedDRA coding system and displayed in tables and data listings using system organ class (SOC) and preferred term (PT). Note that solicited and unsolicited AEs will be analyzed and presented separately. The severity of all AEs will be graded in accordance with the FDA document "Guidance for Industry: Toxicity Grading Scale for Healthy Adult and Adolescent Volunteers Enrolled in Preventive Vaccine Clinical Trials" described in Section 5.

Analyses of AEs will be performed for those events that are considered treatment-emergent, where treatment-emergent is defined per protocol as any AE with onset after the administration of study medication.

All AEs occurring on-study will be listed in subject data listings.

By-subject listings also will be provided for the following: subject deaths, SAEs, AEs leading to withdrawal, solicited local site AEs, solicited systemic AEs, MAAEs, and AESIs.

Solicited AEs are predefined local events at the injection site and systemic events for which the subject is specifically questioned and facilitated by use of memory aides.

The following local AEs will be solicited:

- Arm Pain [CRF term: Pain at Site of Injection]
- Local Tenderness [CRF term: Tenderness at Site of Injection]
- Erythema (Redness) [CRF term: Redness at Site of Injection]
- Induration (Swelling/Firmness) [CRF term: Swelling at Site of Injection]

Note: CRF term in the square brackets refers to the term used on the Adverse Event Case Report Form to capture the local solicited AEs.

The following systemic (non-injection site) AEs will be solicited:

- Subjective Fever [CRF term: Subjective Fever]
- Objective Fever [CRF term: Fever]
- Chills [CRF term: Chills]
- Sweats [CRF term: Sweats]
- Myalgia [CRF term: Myalgia]
- Arthralgia [CRF term: Arthralgia]
- Joint Swelling [CRF term: Joint Swelling]
- Joint Tenderness [CRF term: Joint Tenderness]
- Fatigue [CRF term: Fatigue]
- Gastrointestinal Symptoms (symptoms include nausea, vomiting, abdominal pain, and diarrhea) [CRF terms: Nausea, Vomiting, Abdominal Pain, Diarrhea]
- Mucosal Lesions [CRF terms: Mucosal Lesion, Mouth Ulcer]
- Skin Lesions [CRF terms: Skin Lesion]
- Neurological Symptoms (symptoms include blurry vision, changes in balance or coordination, confusion, disorientation, dizziness, severe headache, shaking or body tremors, slurred speech, tingling or numbness, weakness or feeling weak) [CRF terms: Blurry Vision, Changes in Balance or Coordination, Confusion, Disorientation, Dizziness, Severe Headache, Shaking or Body Tremors, Slurred Speech, Tingling or Numbness, Weakness or Feeling Weak]

Neurological symptoms described above will be considered as solicited neurological AEs. Specific joint related (arthralgia, joint swelling, and joint tenderness) will be considered as solicited rheumatologic AEs; and mouth ulcer or skin/mucosal lesions will be considered as dermatologic AEs.

All TEAEs that cause a subject to seek medical care (including extra visits to the clinical site) are considered to be MAAEs.

Additionally, certain neurologic/hematologic/immunologic diseases are considered as AESIs in the study. Such AESIs include pneumonitis, acute respiratory distress syndrome, multiorgan failure, a hemorrhagic diathesis, certain neurologic events (encephalitis, myelitis, aseptic meningitis, optic neuritis, transverse myelitis, generalized convulsions, Guillain-Barré Syndrome, acute disseminated encephalomyelitis), thrombocytopenia ≥ Grade 2, anaphylaxis, and vasculitides.

Summary tables will be generated for the following:

- Solicited local site AEs within 7 days, and 8 to 14 days following vaccination by Solicited Term and severity
- Solicited systemic AEs within 7 days, and 8 to 14 days following vaccination by Solicited Term and severity
- Solicited neurological AEs within 7 days, 8 to 14 days, 15 to 28 days and up to day 181 following vaccination by Solicited Term and severity
- Unsolicited AEs within 7 days, 8 to 14 days, 15 to 28 days and up to day 181 following vaccination by SOC, PT, relatedness, and severity

- Solicited Rheumatologic AEs within 28 days and up to day 181 following vaccination by Solicited Term and severity
- Solicited Dermatologic AEs within 28 days and up to day 181 following vaccination by Solicited Term and severity
- SAEs up to day 181 by SOC, PT and relatedness
- MAAEs up to day 181 by SOC, PT and relatedness
- AESIs at baseline, and up to day 181 by SOC, PT and relatedness

The number and percentage of subjects with any AE type as described above will be summarized by treatment group and combined PHV01 group. Adverse events are summarized by subject incidence rates; therefore, in these tabulations, each subject will contribute once (i.e., the most related occurrence or the most intense occurrence) to each of the incidence rates in the analysis regardless of the number of episodes. Tabulation by relatedness to study vaccine will be categorized as Related (Definite, Probable, Possible) or Not related; while tabulation by severity will be graded as Grade 1 (Mild), Grade 2 (Moderate), Grade 3 (Severe), Grade 4 (Potentially life-threatening).

Additionally, a symptom score will also be used to summarize solicited local and systemic AEs. The symptom score is a scalar quantity that summarizes the overall severity of a subject's solicited AE experience. The symptom index for a given AE will be defined as individual unique toxicity grades reported for each TEAE multiplied by the duration of the TEAE. The individual symptom indices will then be summed for each subject to obtain their symptom score. Larger scores are indicative, overall, of more severe and/or AEs of longer duration; smaller scores are indicative, overall, of less severe and/or AEs of shorter duration.

If an AE is ongoing at the end of the observation period, the length of the observation period post vaccination will be used in the calculation of symptom index. If the severity is missing for any particular AE, then the corresponding symptom index will also be set to missing.

Symptom scores will be summarized descriptively by treatment group and the combined PHV01 treatment group. Symptom scores will be calculated separately for all solicited local and systemic AEs which started within 14 Days of vaccination. The mean, standard deviation, median, minimum, and maximum values will be tabulated.

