3. STUDY DESIGN

3.1. STUDY ENDPOINTS

3.1.1. Primary Safety Endpoints

- Incidence and severity of solicited injection site AEs (arm pain, local tenderness, erythema (redness), induration (swelling/firmness) and systemic AEs (objective fever, subjective fever, chills, sweats, headache, myalgia, arthralgia, fatigue, nausea, vomiting) and neurological AEs (blurry vision, changes in balance or coordination, confusion, disorientation, dizziness, severe headache, shaking or body tremors, slurred speech, tingling or numbness, weakness or feeling weak) between days 1 and 8, and days 9-15 after vaccination, per treatment group (active vaccination versus placebo) and stratified by relatedness.
- Incidence and severity of unsolicited AEs between days 1-8, days 9-15, and up to day 29 after vaccination, per treatment group (active vaccination versus placebo) and stratified by relatedness.
- Incidence and severity of arthritis and skin/mucosal lesions up to day 29 after vaccination using standard case definitions and stratified by relatedness. This includes where possible quantitative reverse transcription polymerase chain reaction (RT-qPCR) for detection of PHV01 and lesion biopsy for histopathology.
- Incidence of SAEs observed up to day 181 and stratified by relatedness.
- Incidence and severity of MAAEs observed up to day 181 and stratified by relatedness.
- Physical and neurological examination results, vital signs, normal and abnormal clinical laboratory values (hematology and clinical chemistry, urinalysis).
- Incidence of adverse events of special interest (AESIs), to include pneumonitis, acute respiratory distress syndrome, multiorgan failure, a hemorrhagic diathesis, certain neurologic events (encephalitis, myelitis, aseptic meningitis, optic neuritis, transverse myelitis, generalized convulsions, Guillain-Barré Syndrome, acute disseminated encephalomyelitis), thrombocytopenia, anaphylaxis, and vasculitides.

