7.5.1. Analysis Addressing the Primary Study Objective (Safety)

Solicited symptoms occurring during the 28 days following vaccination will be summarized by treatment group and by relatedness. The incidence and severity of solicited AEs to the vaccine over the 28-day follow-up period will be calculated. Presentations will include the number and percentage of subjects with at least 1 local AE, and at least 1 general (systemic) AE, as well as the incidence of each AE individually.

The number of subjects with at least 1 incidence of an unsolicited AE reported up to 28 days after vaccination will also be summarized overall and by treatment group. The severity and temporal relationship of the unsolicited AEs to vaccination will also be assessed. Presentations will also summarize unsolicited AEs by grade and vaccine-relatedness. Serious AEs occurring at any point during the trial will be summarized and relatedness to vaccine will be assessed. The incidence rate of solicited AEs may be compared between each treatment group and placebo using Fisher's exact test and logistic regression.

The level of vaccinemia (on days 1 [at 0 and 6 hours], 2, 4, 8, 15, and 29) and shedding will be assessed on all subjects. The proportion of subjects with detected vaccinemia, as well as the geometric mean and AUC of vaccinemia level, will be presented at each time point where data are collected. The relationship between vaccinemia level and dose will be explored in a mixed model for repeated measures (MMRM) analysis that incorporates dose level, time, and other potential predictive factors. A similar model will be used to explore the relationship between dose and the AUC of the vaccinemia level.

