1.2.5. Safety and Immunogenicity Parameters

1.2.5.1. Safety Parameters

Safety will be assessed by analysis of the occurrence of treatment emergent adverse event (TEAE) and vaccine viremia, as well as by adverse changes in laboratory evaluations (chemistry, hematology, urinalysis, etc.), vital signs, and physical findings, including neurologic examinations. Solicited AEs will be collected systematically through Day 29; unsolicited TEAEs, medically attended adverse events (MAAEs), SAEs, and AESIs will be collected for the entire duration of a subject's participation in the study with the help of Memory Aids reviewed at every visit The primary safety endpoints are:

- Incidence and severity of solicited injection site AEs (arm pain, local tenderness, erythema (redness), induration (swelling/firmness) and systemic AEs (objective fever, subjective fever, chills, sweats, headache, myalgia, arthralgia, fatigue, nausea, vomiting) and neurological AEs (blurry vision, changes in balance or coordination, confusion, disorientation, dizziness, severe headache, shaking or body tremors, slurred speech, tingling or numbness, weakness or feeling weak) between Days 1 and 8, Days 9-15, and up to Day 29 after vaccination, per treatment group (active vaccination versus placebo).
- Incidence and severity of unsolicited AEs between Days 1-8, Days 9-15, and up to Day 29 after vaccination, per treatment group (active vaccination versus placebo) and stratified by relatedness, i.e., not related vs related.
- Incidence and severity of arthritis and skin/mucosal lesions up to Day 29 after vaccination using standard case definitions and stratified by relatedness. This includes where possible quantitative reverse transcription polymerase chain reaction (RT-qPCR) for detection of PHV01 and lesion biopsy for histopathology.
- Incidence of SAEs observed up to Day 181 and stratified by relatedness.
- Incidence and severity of MAAEs observed up to Day 181 and stratified by relatedness.
- Physical and neurological examination results, vital signs, normal and abnormal clinical laboratory values (hematology and clinical chemistry, urinalysis).

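### The SAP's adverse event tables do not fully deliver three primary safety endpoints: relatedness is missing for solicited events and severity for MAAEs

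*SAP*

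**What the plan says.** **Protocol.** Section 3.1.1 defines the primary endpoint on solicited local, systemic and neurological events "between days 1 and 8, and days 9-15 after vaccination, per treatment group (active vaccination versus placebo) and stratified by relatedness". For joint and skin events it asks for "Incidence and severity of arthritis and skin/mucosal lesions up to day 29 after vaccination using standard case definitions and stratified by relatedness". For MAAEs it asks for "Incidence and severity of MAAEs observed up to day 181 and stratified by relatedness". The analysis section, 7.5.1, repeats the first requirement: "Solicited symptoms occurring during the 28 days following vaccination will be summarized by treatment group and by relatedness".

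**SAP endpoint list (1.2.5.1).** The bullet on solicited events no longer mentions relatedness. The bullet on arthritis and skin or mucosal lesions keeps it. The MAAE bullet keeps severity: "Incidence and severity of MAAEs observed up to Day 181 and stratified by relatedness".

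**SAP table list (4.4.2).** The systemic table is specified as "Solicited systemic AEs within 7 days, and 8 to 14 days following vaccination by Solicited Term and severity". The local, neurological, rheumatologic and dermatologic tables differ in their time windows but have the same two dimensions, term and severity. The MAAE table is "MAAEs up to day 181 by SOC, PT and relatedness". The unsolicited table in the same list names both relatedness and severity.

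**The concern.** The trial is first-in-human, and safety is a primary objective. A programmer who builds exactly the tables listed in SAP 4.4.2 would produce no summary by treatment group of related solicited events and none of MAAE severity, although the protocol makes both part of its primary safety endpoints.

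Relatedness is most useful for the non-specific terms, such as dizziness, weakness and arthralgia. The neurological, rheumatologic and dermatologic tables run to day 181, and over six months events unrelated to vaccination can accumulate under those terms. If the omission comes to light only after unblinding, the missing columns become post hoc additions to a primary endpoint.

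**Working it through.** No arithmetic beyond counting applies. The check sets each of the seven primary safety endpoints in Protocol 3.1.1 against the SAP endpoint list and the SAP table list.

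| Endpoint | Protocol 3.1.1 | SAP 1.2.5.1 | SAP 4.4.2 table(s) | Missing from tables |
|---|---|---|---|---|
| Solicited local, systemic, neurological | severity, relatedness | severity | 3 tables: term, severity | relatedness |
| Unsolicited AEs | severity, relatedness | severity, relatedness | 1 table: SOC, PT, relatedness, severity | nothing |
| Arthritis, skin/mucosal lesions | severity, relatedness | severity, relatedness | 2 tables (rheumatologic, dermatologic): term, severity | relatedness |
| SAEs | relatedness | relatedness | 1 table: SOC, PT, relatedness | nothing |
| MAAEs | severity, relatedness | severity, relatedness | 1 table: SOC, PT, relatedness | severity |
| Examinations, vital signs, laboratory | not an AE breakdown | same | not AE tables | not applicable |
| AESIs | incidence | incidence | 1 table: SOC, PT, relatedness | nothing |

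**Counts.** AE summary tables: 3 + 1 + 2 + 1 + 1 + 1 = 9. Solicited tables: 3 + 2 = 5, of which 5 have severity and 0 have relatedness. MAAE tables: 1, with relatedness and without severity. Tables that fall short of the protocol: 5 + 1 = 6 of 9. Endpoints affected: 3 of 7.

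**Two kinds of gap.** For local, systemic and neurological events the SAP is consistent with itself, because relatedness is absent from both 1.2.5.1 and 4.4.2, but it departs from the protocol. For arthritis and skin lesions and for MAAEs the SAP contradicts itself, because 1.2.5.1 promises a breakdown that 4.4.2 does not tabulate.

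**Does anything else in the SAP supply the missing breakdowns?**

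1. The text after the table list in 4.4.2 groups relatedness into Related and Not related, lists the severity grades, and counts each subject once at the most related or most intense occurrence. These are rules for tables that have those dimensions. Reading them as adding relatedness to every solicited table would override a list that names its dimensions table by table.
2. The by-subject listings in 4.4.2 cover solicited local and systemic events and MAAEs. They give individual records, not incidence by group.
3. The symptom score in 4.4.2 multiplies grade by duration. Relatedness does not enter it.
4. SAP 1.1.1 says the SAP will outline differences from the protocol's planned objectives. Section 6 gives only a general statement that changes will be summarized in the study report. The revision history in 8.1 covers only results below the limits of detection and quantitation. The change is recorded in none of these places.

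**The case against.** **The omission may be deliberate.** SAP 1.2.5.1 drops relatedness for solicited events and, in the next bullet, spells out the related/not related split for unsolicited events. That looks like a choice, and Protocol section 7 leaves analysis details to the SAP. This stands for local, systemic and neurological events, where documenting the change is an acceptable remedy. It does not explain the joint and skin events or MAAEs, where the SAP's own endpoint list keeps the breakdown.

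**Part of the information appears elsewhere.** MAAEs are treatment-emergent events that led to medical care. Many will therefore appear with a severity grade in the unsolicited table, which runs to day 181, or in a solicited table. Arthritis is not one of the solicited CRF terms. Under Protocol 6.6.1 a known diagnosis is recorded in place of symptoms for unsolicited events, so an arthritis diagnosis recorded that way would appear with both breakdowns. This stands as well. A reader might infer that MAAE severity cannot be compared across doses at all, and the documents do not support that. What is missing is a summary of severity under the MAAE heading. The argument is weaker for skin lesions, which are a solicited CRF term.

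**Relatedness is not the main separator from background.** Subjects and site staff are blinded, and every AE table is summarized by randomized group, so the placebo comparison does that work. Attribution is supplementary, though not worthless with 6 placebo subjects. When no event is seen, the exact two-sided 95% upper limit is 1 − 0.025^(1/n). For n = 10 this gives 30.85%, which the plan states as 30.9%. For n = 6 it gives 45.9%.

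**Two stronger readings fail.** A reader might take the related Ebola vaccine's rates in Protocol 1.5.1 to mean that most joint and skin events would be background: 3.2/4.5 = 71% for arthritis and 3.2/5.7 = 56% for dermatitis. Each control rate is 3 of 94, with an exact 95% interval of about 0.7% to 9.0%. For arthritis the share could then be as low as 0.7/4.5 = 16%, and the upper limit exceeds the vaccinee rate. The figures also come from a different vaccine, so nothing here rests on them. A reader might also infer that the pausing rule is affected because it refers to relatedness. It is not. The Safety Review Committee reviews day 8 data from each dosing cohort during enrollment, and a physician assigns relatedness to every event whatever the final tables show.

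**Conclusion.** The mismatch is confirmed and moderate in weight. If SAP 4.4.2 is followed as written, parts of three of the seven primary safety endpoints have no planned summary by treatment group: relatedness in five solicited tables and severity in one MAAE table. For two of the three endpoints the SAP is also internally inconsistent, and no departure from the protocol is recorded.

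No data are lost, no estimate is biased and no dosing decision changes. The conclusion assumes that the list in 4.4.2 is complete and that table shells outside these documents do not add the missing columns. If the shells already carry them, only the SAP text needs correcting.

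**What to change.** In SAP 4.4.2:

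- Add Related/Not related, as that section already defines it, to the solicited local, systemic, neurological, rheumatologic and dermatologic tables.
- Add maximum severity to the MAAE table, using the existing rule that each subject counts once at the most intense occurrence.

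In SAP 1.2.5.1, restore the stratification by relatedness to the first bullet, on solicited events.

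If dropping relatedness for local, systemic and neurological events was intended, state and justify that in SAP section 6 instead. That alternative does not cover the joint and skin tables or the MAAE table unless 1.2.5.1 is changed too.

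The cost is a few extra columns in six tables, from data already collected for every event. With 6 to 10 subjects per group many cells will be empty or hold one subject, so the added columns should be read descriptively.

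### SAP 4.4.2 plans no whole-period table for solicited injection-site and general systemic reactions, although Protocol 7.5.1 says that summary will be produced

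*SAP*

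**What the plan says.** Protocol 7.5.1, the analysis for the primary safety objective, states: "The incidence and severity of solicited AEs to the vaccine over the 28-day follow-up period will be calculated". It continues: "Presentations will include the number and percentage of subjects with at least 1 local AE, and at least 1 general (systemic) AE", and also asks for the incidence of each event individually.

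The SAP 4.4.2 table list has "Solicited local site AEs within 7 days, and 8 to 14 days following vaccination by Solicited Term and severity" and "Solicited systemic AEs within 7 days, and 8 to 14 days following vaccination by Solicited Term and severity". No listed table runs from vaccination to day 14 or day 28 for these two classes. Other solicited classes are treated differently in the same list: rheumatologic and dermatologic events are tabulated over 28 days and to day 181, and neurological events in successive windows to 28 days and to day 181.

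The endpoint definitions differ as well. Protocol 3.1.1 sets the solicited endpoint "between days 1 and 8, and days 9-15 after vaccination, per treatment group (active vaccination versus placebo) and stratified by relatedness". SAP 1.2.5.1 sets it "between Days 1 and 8, Days 9-15, and up to Day 29 after vaccination". SAP section 6, which deals with changes to planned analyses, does not mention the 28-day summary.

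**The concern.** Followed as written, the SAP does not produce a summary that the protocol states for its primary safety objective. The two planned tables cannot be combined to recover it, because a subject with a reaction in each window is counted once in each.

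Two results are affected for injection-site and general systemic terms (fever, chills, sweats, myalgia, fatigue, gastrointestinal symptoms). One is the proportion of subjects at each dose with any reaction. The other is the distribution of subjects by their worst grade. Protocol 7.2 and SAP 3.12 say the interim analysis is to guide dose selection for the next trial, and these are natural tolerability figures to set beside the immunogenicity results. Protocol 7.5.1 also allows Fisher's exact test of solicited incidence against placebo, which needs one defined outcome per subject.

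**Working it through.** **The plan's own figure.** No stated number is in dispute. The only stated precision for an AE rate (Protocol 7.1, SAP 3.1) is the upper 95% Clopper-Pearson limit when no event is seen. For 0/10 this is 1 − 0.025^(1/10) = 30.8%, against 30.9% stated. For 0/30 it is 11.6%, as stated in the SAP. Both reproduce to within 0.1 point.

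**Do the windows match?** SAP 3.2 makes the dosing day Day 1. So 0–7 days after vaccination is Days 1–8, 8–14 days after is Days 9–15, and 28 days after is Day 29. Hence:

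| Source | Period for local and general systemic terms |
|---|---|
| Protocol 3.1.1 | Days 1–8; Days 9–15 |
| Protocol 7.5.1 | one 28-day period |
| SAP 1.2.5.1 | Days 1–8; Days 9–15; up to Day 29 |
| SAP 4.4.2 tables | 0–7 days; 8–14 days |

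The SAP tables match Protocol 3.1.1 and do not match Protocol 7.5.1.

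**Does anything else in SAP 4.4.2 supply the rate?** The sentence on counting subjects with any AE type refers back to the types already listed and adds no window. The symptom score does span 14 days, but it sums grade times duration and is not a proportion of subjects.

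**What the two tables determine.** Let *a* of *n* subjects react in the first window, *b* in the second and *c* in both. The whole-period count is *a* + *b* − *c*. The tables do not give *c*, which can be anything from max(0, *a* + *b* − *n*) to min(*a*, *b*). So the count lies between max(*a*, *b*) and min(*a* + *b*, *n*).

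Group sizes are 10 per dose, 6 placebo and 30 pooled (Protocol 7.1). The event counts below are assumptions; the documents give none.

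| *a*, *b* (*n* = 10) | Whole-period count | Rate |
|---|---|---|
| 7, 2 | 7 to 9 | 70–90% |
| 4, 2 | 4 to 6 | 40–60% |
| 5, 3 | 5 to 8 | 50–80% |
| 5, 5 | 5 to 10 | 50–100% |
| *a*, 0 | *a* | fixed |

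The widest possible gap is 5 of 10 in a dose group, 3 of 6 in placebo and 15 of 30 pooled: 50 points in each case. The gap is zero when one window is empty.

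**Severity.** The highest grade seen in a group is the higher of the two windows' maxima, so it is recoverable. The number of subjects at each worst grade over the whole period is not, for the same reason as the rate.

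**The case against.** The strongest reply is that the SAP follows the endpoint. Protocol 3.1.1 defines the solicited primary endpoint in exactly the two windows that SAP 4.4.2 tabulates. That stands. A reader might infer that a primary endpoint goes uncomputed, and the documents do not support it: what is missing is the summary stated in Protocol 7.5.1.

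A reader might also infer that the SAP contradicts its own endpoint because of "between Days 1 and 8, Days 9-15, and up to Day 29 after vaccination". That is not clear. The bullet combines local, systemic and neurological events, and only neurological, arthritis and rash events are solicited after Day 15. The phrase may refer to the neurological terms, which do have later tables. For the same reason the 28-day wording in Protocol 7.5.1 fits local and general systemic terms loosely; the useful whole-period rate for them is mainly a 0–14 day rate.

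A third tempting reading is that the rate can never be known. By-subject listings of solicited local and systemic events are planned, and with 36 subjects the count could be made by hand. The interim-analysis text in SAP 3.12 also names no window. What is missing is a planned table, not the data.

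A fourth is that a late fever or fatigue would drop out of every table, because the SAP says: "Note that solicited and unsolicited AEs will be analyzed and presented separately". Since those terms are no longer solicited after Day 15, they most naturally fall into the unsolicited tables, which run to day 181. A sentence saying so would only clarify.

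Finally, the realised gap may be small. For the related Ebola vaccine, Protocol 1.5.1 puts early systemic reactions generally within 12 to 24 hours, and it expects acute-phase reactions to PHV01 within the first 1–3 days. If few subjects react in the second window, the bounds nearly coincide. This limits the likely size but does not remove the mismatch.

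**Conclusion.** The point holds in a limited form. For injection-site and general systemic reactions, the SAP table list omits the cumulative summary stated in Protocol 7.5.1, and no departure is recorded. Joint, skin or mucosal and neurological terms are outside the gap because each has a longer-period table.

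The size depends on how many subjects react in both windows, which cannot be known in advance. Under the assumed 7/10 and 2/10, the rate is left open over 20 points. The arithmetic ceiling is 50 points, and zero is possible. The timing expected in Protocol 1.5.1 points to the lower end.

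This is a correctable conflict between documents, worth settling before the dose-selection tables are run. It does not undermine the endpoint in Protocol 3.1.1 or the data collection.

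**What to change.** 1. In SAP 4.4.2, add cumulative tables over the full solicitation period (0 to 14 days after vaccination), by treatment group and combined PHV01 group: number and percentage of subjects with any solicited local AE, with any solicited systemic AE, and with each term by maximum grade. Keep the two existing windows.
2. Either add the 28-day summary stated in Protocol 7.5.1, or record in SAP section 6 that it is not being produced for these terms and why.
3. Reconcile the periods in Protocol 3.1.1, Protocol 7.5.1 and SAP 1.2.5.1, and say which terms the phrase about Day 29 covers.
4. Optionally, state that a solicited-term event starting after its solicitation window counts as unsolicited.

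Cost: SAP wording and one extra column set. No new data are needed.
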